8.6.6 Analysis of exploratory endpoint(s)

Not applicable.

Safety analysis

This section describes the safety analyses that will be conducted on the treatment and follow-up periods (i.e., the safety analyses on all data collected during the treatment and follow-up periods and all data collected in subjects who dropped-out during the treatment and follow-up periods).

All definitions relative to safety endpoints (primary endpoints) are detailed in section 4.1.

Safety analyses will be conducted on the safety population and will be performed for all safety variables specified below.

All safety data will be summarized by treatment group.

The safety analyses of changes from baseline to a specific time point in safety variables (e.g., laboratory parameters, physical examinations, vital signs) will only include subjects from the safety population who have data available for both the baseline and the time point under considerations unless otherwise specified.

No statistical tests will be performed on the safety endpoints.

8.7.1 Adverse events

All AEs will be classified by Primary SOC and Preferred Term according to the MedDRA Version 23.0 or higher. The occurrence of AEs and SAEs following administration of ADM03820 to the final follow-up visit will be categorized as solicited adverse events, unsolicited adverse events and lab abnormalities. A summary table will be provided to summarize the frequencies and percentages of each category and overall by treatment group. Subsequent analyses will be conducted for each category, respectively, by severity, relationship to study medication, and by MedDRA level hierarchy (SOC and Preferred Term).

The occurrence of changes from baseline in physical examination, vital signs and clinical safety laboratory values following administration of ADM03820 to the final follow-up visit will be summarized descriptively by treatment group. AEs will be collected at Day 1 during and after dosing. Any medical condition that is present at the time that the subject is screened should be considered as baseline and not reported as an AE. However, if the condition increases in severity or frequency at any time during the study, it will be recorded

as an AE. Severity and relationship to the treatment will be assessed by investigator: severity is graded according CTCAE v5.0; relationship to the treatment is categorized as not related, possibly related, and definitely related.

Where a subject has the same adverse event, based on preferred terminology, reported multiple times in the treatment period, the subject will only be counted once at the preferred terminology level in adverse event frequency tables. Where a subject has multiple adverse events within the same system organ class in the treatment period, the subject will only be counted once at the system organ class level in adverse event frequency tables. Under both scenarios, the event of the worst severity or the worst-case relationship assessment will be used for summarizing safety endpoints.

AEs will be followed until resolution or stability even if this extends beyond the study-reporting period. Resolution of an AE is defined as the return to pretreatment status or stabilization of the condition with the expectation that it will remain chronic. Follow-up procedures, evaluations, and outcomes will be recorded on the subject's case report forms and will be presented using individual patient listings.

Details for imputing missing or partial start dates of adverse events are described in section 7.2.2.

In summaries by SOC and Preferred Term, adverse events will be sorted by descending frequency within each SOC and Preferred Term according to the total number of events. In summaries by Preferred Term, AEs will be sorted by decreasing frequency according to the total number of events.

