3.2. Study Outcome Measures

3.2.1. Primary Endpoints

- The occurrence of Serious Adverse Events following administration of ADM03820 to the final follow-up visit.
- The occurrence of Adverse Events from administration of ADM03820 to the final follow-up visit.

²⁰ Eroshenko, N., Gill, T., Keaveney, M. Church, et al., Implications of Antibody-Dependent Enhancement of Infection for SARA-CoV-2 Countermeasures. *Nature biotechnology*. 05 June 2020. https://www.nature.com/articles/s41587-020-0577-1

• The occurrence of changes from baseline in physical examination, vital signs and clinical safety laboratory values following administration of ADM03820 to the final follow-up visit.

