4. STUDY DESIGN

This is a Phase 1, randomized, double-blind, placebo-controlled study of five dose cohorts to evaluate the safety, tolerability, and immunogenicity of ADM03820 in healthy adults. This is a first-in-human study and each subject will receive a single dose of ADM03820 or placebo.

The study will randomize a total of 50 healthy subjects to receive an intramuscular (IM) injection of either ADM03820 or placebo.

Cohort	Dose of ADM03820	Number of Subjects
1	150 mg IM injection	10 subjects (8 active, 2 placebo)
2	300 mg IM injection	10 subjects (8 active, 2 placebo)

Table 1: Cohorts

3	300 mg IM injection	10 subjects (8 active, 2 placebo)
4	300 mg IM injection	10 subjects (8 active, 2 placebo)
5	600 mg IM injection	10 subjects (8 active, 2 placebo)

Schedule for Subjects

Subjects in cohorts 1-4 will participate in the study for approximately 554 days, including a 14day screening period. Subjects in cohort 5 will participate in the study for approximately 379 days, including a 14-day screening period. All subjects in the study will have a 24-hour stay in the clinic after dosing is complete to ensure that no hypersensitivities or safety signals occur. Follow-up outpatient visits for all cohorts will occur on Days 3, 4, 8, 15, 30, 45, 60, 90,120, 150, 180, and 365 with cohorts 1-4 having additional telephone visits on Days 450 and 540. The last outpatient follow up visit is scheduled at Day 365. The end of the study is defined as the date of the last visit of the last subject in the study.

There are several blinded interim analyses planned for this study. A blinded interim analysis is planned to analyze all PK samples through Day 30 for all subjects in Cohorts 1-2. A second blinded interim analysis is planned to analyze all PK samples after all subjects in Cohorts 1-3 complete Day 60. A third interim analysis is planned to analyze safety and PK after all subjects in cohort 5 complete Day 60.

There is also an interim clinical study report (CSR) planned after subjects in Cohorts 1 through 4 complete Day 90.

Schedule for Cohorts

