8.16. Visit 16: Telephone Visit (Day 450 ±5) for Cohorts 1-4

- Review and update concomitant medications
- Assessment of Aes and SAEs
- Counsel all subjects on the prevention of COVID-19
- Counsel both men and women of child-bearing potential on the avoidance of pregnancy

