8.17. Visit 17: Telephone Visit (Day 540 ±5) for Cohorts 1-4

- Review and update concomitant medications
- Assessment of Aes and SAEs
- Counsel all subjects on the prevention of COVID-19

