11.3.3. Safety Analysis Plan

11.3.3.1. Adverse and Serious Adverse Events

AEs will be coded using Medical Dictionary for Regulatory Activities[®] (MedDRA). All AEs that occur after the initiation of study medication will be summarized using frequency counts and percentages. Summaries will be presented by dose cohort and control group. The following summaries will be presented for AEs and SAEs:

- Overall (i.e., regardless of severity or relationship to treatment)
- By CTCAE v5.0
- By relationship to study medication
- By MedDRA level hierarchy (system organ class and preferred term)

Unless otherwise specified, at each level of subject summarization in reporting the incidence of the AEs, a subject will be counted once if the subject reported one or more events. If more than one occurrence of an event is reported, the event of the worst severity or the worst-case relationship assessment will be summarized.

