8. A urine dipstick will be done to evaluate for presence of protein, glucose or blood in urine. If dipstick is abnormal, a complete urinalysis with microscopic will be performed.

9. A 12-lead ECG will be performed during screening and post dose performed 30 minutes (±10 minutes) after completion of dosing.

10. Viral Serology includes HIV, HBsAg and antibody to HCV.

11. PK samples will be taken at the following times: pre-dose, 2, 4, 8, and 24 hours post injection and on days 2, 3, 4, 8, 15, 30, 45, 60, 90, 120, 150, 180, and 365 for all cohorts

12. Serum from subjects who give consent for future use samples will be collected at 2 hr and 4 hr post dose and on days 2, 8, and 30

13. Vital signs (sitting for at least 10 minutes) will be checked just before injection and every visit.

14. The subject will be under direct observation during at least the initial 30 minutes of dosing. A physical examination will be performed at approximately 30 minutes post injection or in response to subject symptoms which will include the following: General appearance including alertness, diaphoresis, chills, and any difficulty breathing, HEENT, Chest, Heart, Skin and Joints

15. Draw prior to dosing at baseline

16. The Hypersensitivity Panel includes cytokine and complement panels, IgE, and tryptase. Draw 14ml prior to dosing. If a subject develops anaphylaxis or anaphylactoid reaction, an additional 10 mL sample will be drawn during the event and another will be drawn after the event

Protocol: ADM03820-001

Version 6.0 July 14, 2022

- 17. Subjects in all cohorts will receive RT-PCR testing at screening, Day 1 prior to dosing, and at presentation of symptoms.
- 18. SARS-CoV-2 antibodies will only be tested in Cohorts 1-4 (Not applicable for Cohort 5).

19. TC visits will be conducted for only Cohorts 1-4 (Not applicable for Cohort 5).

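### By-dose-cohort AE and SAE percentages cover scheduled follow-up to Day 540 in Cohorts 1-4 but only to Day 365 at 600 mg, and the SAP text sets no common cut-off (minor)

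*SAP*

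**What the plan says.** - **Endpoint window.** Protocol 3.2.1 defines the primary AE endpoint as "The occurrence of Adverse Events from administration of ADM03820 to the final follow-up visit". SAP 8.7.1 uses the same end point: "The occurrence of AEs and SAEs following administration of ADM03820 to the final follow-up visit will be categorized as solicited adverse events". Neither names a day.
- **Data used.** The SAP's Safety analysis section, printed just before 8.7.1, opens: "This section describes the safety analyses that will be conducted on the treatment and follow-up periods". It includes all data from both periods.
- **Table columns.** Protocol 11.3.3.1 asks for frequency counts and percentages: "Summaries will be presented by dose cohort and control group". The SAP instead summarizes all safety data by *treatment group*, which it does not define.
- **Length of follow-up.** Protocol section 4 gives outpatient visits to Day 365 for everyone, "with cohorts 1-4 having additional telephone visits on Days 450 and 540". Protocol 8.16 ("Telephone Visit (Day 450 ±5) for Cohorts 1-4") and 8.17 ("Telephone Visit (Day 540 ±5) for Cohorts 1-4") both include assessment of AEs and SAEs. Footnote 19 of Appendix A confirms it: "TC visits will be conducted for only Cohorts 1-4 (Not applicable for Cohort 5").
- **SAEs after the last visit.** Protocol 9.3.2 collects SAEs for up to 60 days after each subject's last study visit.
- **Endpoints with a fixed window.** In SAP 8.6.5, the three COVID-19 incidence endpoints stop at Day 365 in all cohorts.

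**The concern.** A subject counts once in an AE table however many events occur, so a longer window can raise a crude percentage but not lower it. Cohorts 1-4 are asked about AEs for 175 days longer than Cohort 5. Even with no dose effect, by-cohort tables would then tend to show a lower percentage at 600 mg than at 150 or 300 mg. The same holds against pooled placebo, where 8 of 10 subjects are followed to Day 540.

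The primary objective is the safety and tolerability of different doses, and the artefact favours the highest dose. The SAP text gives no common cut-off, person-time rate or time-to-event summary for AEs that would remove it.

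**Working it through.** **1. The plan's own figures.** Protocol 11.1 and SAP 4.0 take 8 active subjects and true event rates of 0.15 to 0.5.
- P(at least one event) = 1 - (1 - p)^8, which gives 0.7275 at p = 0.15 and 0.9961 at p = 0.5. The plan states 0.728 and 0.996.
- Exact 95% upper bound for 0/8 = 1 - 0.025^(1/8) = 0.369, as stated.

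Both reproduce. Neither rate is tied to a time window.

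**2. The windows.**
- Scheduled AE review: 540 - 365 = 175 days; 540/365 = 1.48.
- SAEs with the 60-day extension: 540 + 60 = 600 and 365 + 60 = 425. The difference is again 175 days; 600/425 = 1.41.
- Placebo: 4 × 2 = 8 of 10 subjects go to Day 540. Active: 4 × 8 = 32 of 40. Both are 80%.

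**3. Size of the gap with no dose effect.** The documents do not give event timing, so this step rests on assumptions. Let b be the reported event rate on Days 366-540 as a fraction of the mean rate on Days 1-365. Early clustering and telephone-only contact both lower b. The plan's 0.15 to 0.50 is borrowed as the risk, anchored at Day 540 or at Day 365.

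- f = 1 + b × 175/365
- Day 540 anchor: P365 = 1 - (1 - P540)^(1/f)
- Day 365 anchor: P540 = 1 - (1 - P365)^f

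At b = 1, Day 540 anchor: 0.15 becomes 0.104, and 0.50 becomes 0.374. At b = 1, Day 365 anchor: 0.15 becomes 0.214, and 0.50 becomes 0.641.

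Gap between Cohorts 1-4 and 600 mg in percentage points (Day 540 anchor / Day 365 anchor):

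| b | f | risk 0.15 | risk 0.30 | risk 0.50 |
|---|---|---|---|---|
| 1 (approximate ceiling) | 1.479 | 4.6 / 6.4 | 8.6 / 11.0 | 12.6 / 14.1 |
| 0.5 | 1.240 | 2.7 / 3.2 | 5.0 / 5.7 | 7.2 / 7.7 |
| 0.2 | 1.096 | 1.2 / 1.3 | 2.2 / 2.4 | 3.1 / 3.2 |
| 0 (all onsets early) | 1 | 0 | 0 | 0 |

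The ceiling is 0.4 to 1.1 of 8 subjects; at b = 0.2 it is 0.1 to 0.3. Against pooled placebo each gap is multiplied by 0.8, so the ceiling is 3.7 to 10.1 or 5.1 to 11.3 points.

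**4. Against sampling error.** The exact 95% interval for 4/8 is 16% to 84%, far wider than any entry in the table.

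**5. Effect of a Day 365 cut.** The window ratio becomes 365/365 = 1. The cut needs a rule for partial dates, because SAP 6.0 sets a missing onset day to the first of the month and a missing month to January 1 (outside the month or year of dosing). Illustration: a subject dosed on 20 July 2021 has an onset on Day 370 (24 July 2022). If the day is missing, the date becomes 1 July 2022, which is Day 347. An onset on Day 450 (12 October 2022) with the month missing becomes 1 January 2022, which is Day 166. Both would fall on the wrong side of the cut.

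**The case against.** **Columns.** The artefact needs by-cohort columns, and the SAP says *treatment group*. Its disposition text (section 7.0) and PK population (section 5.0) name cohort and treatment group separately, which suggests active versus placebo. The Kruskal-Wallis comparison in 8.6.5 points the other way. If active versus placebo is meant, 80% of each arm goes to Day 540 and the artefact disappears. This stands, but the doses are then pooled, contrary to Protocol 11.3.3.1, and the SAP's list of changes does not record it. The table templates are a separate document not available here and may settle both columns and cut-off.

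**SAEs at 600 mg.** A reader might infer that no 600 mg event after Day 365 can count. The documents do not support that for SAEs. Protocol 9.3.2 collects them to about Day 425 in Cohort 5, and 11.3.3.1 counts AEs after dosing with no end date. The endpoint wording in Protocol 3.2.1 and SAP 8.7.1 would stop at the final visit, so their status is ambiguous. The 175-day difference is unaffected.

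**A hidden cut-off.** SAP 8.7.1 counts repeat events within a *treatment period*. The term is undefined in this single-dose study, and the Safety analysis section includes follow-up, so it supplies no cut-off, though it adds uncertainty.

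**Comparability.** Randomization is within cohort, and Cohort 5 actives share a window with their own two placebo subjects. Cohort 5 also admitted seropositive and previously vaccinated subjects. This stands: equal windows remove only one source of difference.

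**Importance.** No safety tests are planned, and listings present individual data. Events are also tabulated by severity and relationship. Days 366-540 have two telephone contacts and no scheduled laboratory tests, vital signs or examinations. The Day 8 safety reviews and the Day 60 Cohort 5 interim fall within follow-up that all cohorts share. All this limits the consequence without correcting the final tables.

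**Conclusion.** The point holds for the tables that Protocol 11.3.3.1 requires. Scheduled follow-up is 175 days shorter at 600 mg than in the other cohorts, and the SAP text does not equalize it. The direction is clear: it tends to lower the 600 mg percentage. The size is not known. It is zero if all onsets are early. Under an assumed constant rate and risks of 0.15 to 0.50, the ceiling is about 5 to 14 points. It is probably much smaller, and it is below sampling error with 8 subjects.

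A reader might take the ceiling as an expected bias, or conclude that the 600 mg safety comparison is invalid. The documents support neither: they give no event timing, the tables are descriptive, and the cross-cohort comparison is non-randomized with or without equal windows. Priority: minor.

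**What to change.** Add to SAP 8.7.1:

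> AE and SAE tables will have a column for each dose cohort and one for control. Between-dose tables will count events with onset from dosing through Day 365 in every cohort. All AEs and SAEs with onset after Day 365 in any cohort, including SAEs collected up to 60 days after the last study visit, will be summarized separately by cohort and listed. An event whose partial onset date could fall on either side of Day 365 will be classified by the visit at which it was first reported.

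Also:
- Record the Day 365 table under SAP 8.0, Changes to Planned Analysis.
- State whether SAEs after the last visit belong to the primary endpoint, so that Protocol 3.2.1, 9.3.2 and 11.3.3.1 and SAP 8.7.1 agree.
- Reconcile the Cohort 5 follow-up to Day 379 in SAP 3.0 with the Day 365 last visit in the protocol. The protocol's 379 days of participation include the 14-day screening (14 + 365 = 379).

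**Cost.** Four SAP sentences, one entry under changes, and a filter on study day, which the SAP already derives. The downsides are extra tables and that late Cohort 1-4 events leave the main dose comparison, though they stay in the separate summary. The ±5-day window at Visit 15 leaves a mismatch of at most 5 days.

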9.2. Methods and Timing for Assessing, Recording, and Analyzing Safety Parameters

9.2.1. Adverse Events

Adverse events will be collected at Day 1 during and after dosing. Any medical condition that is present at the time that the subject is screened should be considered as baseline and not reported as an AE. However, if the condition increases in severity or frequency at any time during the study, it should be recorded as an AE.

All Aes must be graded for severity and relationship to study product based on the Investigator's assessment.

Severity of adverse events will be graded using CTCAE v5.0 (Appendix B).

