9.2.2. Relationship to Study Product

Aes and SAEs must be assessed by the investigator to determine relationship to study product. All Aes must have their relationship to study product assessed using the following terms. In a clinical trial the study product must always be suspect.

- **Definitely Related:** There is a definite probability that the study product caused the adverse event.
- **Possibly Related:** There is a reasonable possibility that the study product caused the adverse event. Reasonable possibility means that there is evidence to suggest a causal relationship between the study product and the adverse event

• **Not Related**: There is not a reasonable possibility that the administration of the study product caused the event

To help assess, the following factors may be considered:

- Temporal relationship of the event to the administration of study product;
- Whether an alternative etiology has been identified;
- Biological plausibility;
- Existing therapy and/or concomitant medications.

9.3. **Reporting Procedures**

9.3.1. Adverse Events:

Aes not meeting the criteria for "SAEs," will be captured on the appropriate case report form. Information to be collected for Aes includes event description, date of onset, investigator assessment of severity, relationship to study product, date of resolution of the event, seriousness, and outcome.

All Aes will be followed until resolved or considered stable by the investigator.

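### SAP 8.7.1 plans severity, relationship and organ-class summaries only within AE categories, one of them undefined, where the protocol requires them over all AEs and SAEs

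*SAP*

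**What the plan says.** SAP 8.7.1 states that AEs and SAEs after dosing "will be categorized as solicited adverse events, unsolicited adverse events and lab abnormalities". It then plans one top-level display: "A summary table will be provided to summarize the frequencies and percentages of each category and overall by treatment group". The detailed tables follow by category: "Subsequent analyses will be conducted for each category, respectively, by severity, relationship to study medication", and also by MedDRA system organ class (SOC) and preferred term (PT). The rest of the section gives counting and sorting rules. It does not state a combined version of the detailed tables.

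Protocol 11.3.3.1 is organised differently. It says "All AEs that occur after the initiation of study medication will be summarized using frequency counts and percentages", and then: "The following summaries will be presented for AEs and SAEs", listing overall, by CTCAE grade, by relationship and by SOC/PT. It has no solicited/unsolicited division. A subject counts once at each level of summary, at worst severity or worst relationship.

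On collection, Protocol 9.2.1 says only "Adverse events will be collected at Day 1 during and after dosing". Protocol 9.3.1 sets out the data fields: "Information to be collected for Aes includes event description, date of onset, investigator assessment of severity, relationship to study product", followed by resolution date, seriousness and outcome.

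SAP section 8.0, which records changes from the protocol's planned analysis, lists the added per-protocol population and nothing else.

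**The concern.** Two things do not fit together. First, the SAP creates a solicited category that the protocol does not define. A programmer working from these two documents could not decide which events belong in it. Second, the SAP attaches the detailed breakdowns to the categories, while the protocol attaches them to all AEs and all SAEs.

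Safety is the primary objective. A reader of a Phase 1 safety report will want to know how many subjects in each dose group had any event of a given grade, any event judged related, or any event in a given organ class. Those counts must be taken over all AEs together, with each subject counted once. If the SAP is followed as written, no table is specified that shows them, and nothing tells the reader that the protocol's tables were replaced.

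**Working it through.** **1. The plan's own figures.** The plan gives no figure on this point. Its only safety precision figures are in the sample size sections, and they reproduce with 8 active subjects per cohort:

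- P(at least one event) = 1 − (1 − p)^8, which is 0.7275 at p = 0.15 and 0.9961 at p = 0.5 (stated: 0.728 and 0.996).
- Exact 95% upper bound with no events = 1 − 0.025^(1/8) = 0.3694 (stated: 0.369).

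The finding does not depend on them.

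**2. Is a solicited event defined anywhere?** The places where it could be defined are:

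- Protocol 9.2.1 (collection): general collection; no term list and no solicitation window.
- Protocol 9.3.1 (data fields): no solicited/unsolicited field.
- Protocol section 8 (visits): a general AE and SAE assessment; no diary.
- Protocol Appendix A (schedule): rows for AE review and SAE review only.
- Protocol 15.2 (data capture): reactogenicity data are named among the data entered, separately from AEs. No procedure, terms or window are given for them elsewhere.
- SAP 8.7.1: uses the category without defining it.

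So there is one trace of a solicited data stream and no definition behind it.

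**3. Which tables does each document specify?**

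| Summary | Protocol 11.3.3.1 | SAP 8.7.1 |
|---|---|---|
| Any AE, all AEs combined | Yes | Yes (overall entry) |
| By grade, all AEs combined | Yes | Per category only |
| By relationship, all AEs combined | Yes | Per category only |
| By SOC/PT, all AEs combined | Yes | Per category only |
| By grade, relationship and SOC/PT for SAEs | Yes | Not specified separately |

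**4. Do the categories overlap?** They can. One subject may have events of different kinds. In addition, the AE definition in Protocol 9.1 covers abnormal laboratory findings, so one finding could be both an unsolicited AE and a laboratory abnormality. No rule assigns it to one category.

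**5. Can the combined counts be recovered from category tables?** Suppose a of 8 active subjects appear in one category table at a given grade or above, and b of 8 in another. The number of distinct subjects lies between max(a, b) and min(8, a + b). The counts below are assumed for illustration; neither document gives an overlap rate.

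| a | b | Distinct subjects | Percentage of 8 |
|---|---|---|---|
| 1 | 1 | 1 to 2 | 12.5% to 25% |
| 2 | 2 | 2 to 4 | 25% to 50% |
| 3 | 3 | 3 to 6 | 37.5% to 75% |

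The overall any-AE count caps the combined figure but does not determine it, because it ignores grade and relationship.

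**The case against.** The best defence is that the combined tables may still be intended. SAP 8.7.1 classifies all AEs by SOC and PT, and its counting and sorting rules are not restricted to a category. Table shells are kept in a separate document (SAP 1.0) and may include combined tables. SAP 8.0 does not say that the protocol's tables were dropped. This shows that deliberate removal is not established. It does not supply the missing specification: the only sentence that plans severity and relationship summaries ties them to each category.

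Several stronger readings are tempting, and the documents do not support them.

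- A reader might infer that the trial collects no solicited events. Protocol 15.2 names reactogenicity data, and the case report form is not available here. What can be said is that solicited events are undefined and no procedure for them is given.
- A reader might infer that the solicited table must be empty, or will be filled after the data are seen. Form or table specifications may fix membership beforehand.
- A reader might infer that the primary endpoint goes unreported. The AE endpoint is occurrence, and the planned overall frequency covers any-AE incidence. Severity and relationship counts are supporting summaries.
- A reader might infer an error of 12.5 percentage points (1/8) for each subject who appears twice. That arises only if someone adds percentages across category tables, which neither document proposes.

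It is also fair to say that the safety analysis has no hypothesis tests, that individual listings are planned, and that the Safety Review Committee works from unmonitored and uncoded data against the criteria in Protocol 9.5. Dose escalation therefore does not rest on these tables. With 50 subjects the combined counts could be rebuilt by hand from listings, but that does not replace a pre-specified table.

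**Conclusion.** The point holds as an undeclared departure from Protocol 11.3.3.1. As written, SAP 8.7.1 leaves one of three categories without defined content. It specifies no table of subjects by worst grade, by relationship or by SOC/PT across all AEs, and none of these for SAEs as a group.

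The size is a matter of lost information, not of bias. In a cohort with 8 active subjects, category counts of 2 and 2 are compatible with a combined incidence of 25% to 50%, and counts of 3 and 3 with 37.5% to 75%. These ranges rest on assumed counts.

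The conclusion assumes that the SAP text governs. If the separate table shells already contain the combined tables, the remaining work is to make the SAP agree with them and to settle the solicited category.

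**What to change.** In SAP 8.7.1:

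- Restore the Protocol 11.3.3.1 tables (overall, by CTCAE grade, by relationship, by SOC/PT) for all AEs combined and, separately, for all SAEs. Count each subject once at each level, at worst grade or worst relationship.
- Keep laboratory findings that are reported as AEs in these tables, and show graded laboratory values additionally under SAP 8.7.2. Moving every laboratory abnormality out of the AE tables would remove events that Protocol 9.1 counts as AEs.
- Delete the solicited/unsolicited split. If reactogenicity is to be shown separately, define it by a fixed preferred-term list and time window before unblinding, present it as a supplementary display, and declare it in SAP 8.0.

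The cost is SAP wording and table shells. The restored tables need no new data.
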